**THE EFFECT OF REPOSITIONING FREQUENCY DETERMINED ACCORDING
TO BODY MASS INDEX ON PRESSURE ULCER DEVELOPMENT TIME:
RANDOMIZED CONTROLLED TRIAL**

ClinicalTrials.gov ID: [NCT05504980](https://clinicaltrials.gov/ct2/show/NCT05504980)

Document Date: June 30, 2023

Setting/Participants

This study was conducted in the intensive care and palliative care units of a university hospital between 01.07.2022 - 29.01.2023. The sampling volume that should be included in the sample of the study was calculated using power analysis; considering the margin of error ($\alpha= 0.05$), effect size ($f= 0.347$) and power 80% ($1-\beta= 0.80$) values and research design, the sample calculation was made for the Chi-Square test and a total of 66 people were determined. Considering the losses, the number of patients included in the sample was planned to be 86 patients (43 intervention group, 43 control group), 30% above the calculated value, and the study was completed with 71 patients. According to body mass index, weight status was stratified into four groups as underweight ($\leq 18.49 \text{ kg/m}^2$), normal weight (18.5 kg/m^2 - 24.9 kg/m^2), overweight (25kg/m^2 - 29.9kg/m^2) and obese ($\geq 30\text{kg/m}^2$).

Body Mass Index	Intervention Group	Control Group
Underweight	1	1
Normal Weight	8	12
Overweight	17	14
Obese	11	7
Total	37	34
General Total		71

Statistical Analysis

Statistical analysis of the research data was performed in the "Statistical Package for the Social Sciences (SPSS) 25.0" statistical package program (PASW Inc., Chicago. IL.USA) under the supervision of a statistical expert. In descriptive statistics; number and percentage distributions were shown and mean (mean) \pm standard deviation (SD) values were given. Demographic quantitative data were compared between the groups by Mann Whitney U test. The distribution of qualitative characteristics of the patients in the groups was analyzed using Pearson Chi-square test or Fisher's exact probability test. "Kaplan Meier - Survival Time" analyses were performed for the duration of pressure ulcer development. General Linear model analysis was performed for effect size. For repeated measures, changes in groups were

analyzed using the nonparametric Brunner Langer (F1 LD F1 model) method. Since only one patient in the intervention group developed pressure ulcers, intra-group statistical analysis could not be performed. The results were evaluated at 95% confidence interval and $p<0.05$ significance level.

Results

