
Socio-demographic characteristics, data on health status, pressure injury development risk assessment scale score, averages of some laboratory findings, and interface pressure values measured from pressure points of patients in the intervention and control groups in intensive care clinics are homogeneously distributed. Pressure injuries developed in 2.70% of the patients in the intervention group and 14.70% of the patients in the control group, the difference between them wasn't statistically significant ($p=0.098$). The effect size is 0.216 and has a low/medium effect size. Injury development time was 16 days in the intervention group and 6.00 ± 2.0 days in the control group (earliest 3rd day, latest 8th day), the difference between them was not statistically significant ($p=0.137$). Pressure injury developed in one underweight, one normal weight, and three obese patient in the control group and one obese patient in the intervention group, the difference between them was statistically significant ($p=0.006$).

In the control group, one patient with underweight, one patient with normal weight and three patients with overweight developed pressure injuries and the difference between them was statistically significant ($p=0.003$). Since only one of the obese patients in the intervention group developed pressure injuries, the development of pressure injuries according to body mass index could not be evaluated. The risk of pressure injury development is higher in underweight and obese patients, and less in overweight patients.

Pressure injuries developed in the gluteal area and sacrum in the patient in the intervention group, and in the sacrum in 8.8% of the patients in the control group, there was no statistically significant difference between them ($p=0.143$).

Conclusion

It was concluded that the frequency of position changes should be done with a personalized program for each patient, not at routine two-hour intervals, and the risk of pressure injury development is higher in low-weight and obese patients, while it is less in overweight patients.

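### The unlabelled p=0.137 for injury development time matches a large-sample rank test of 1 versus 5 injured patients, for which the exact two-sided p-value is 0.333 and cannot be lower

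*Combined protocol and SAP*

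**What the plan says.** The Results section gives "Injury development time was 16 days in the intervention group" and "6.00 ± 2.0 days in the control group (earliest 3rd day, latest 8th day". It calls the difference not statistically significant, with p=0.137. It names no test and does not say whether the p-value is exact or asymptotic.

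The numbers behind the two summaries are very small. The Statistical Analysis section explains that an intra-group analysis could not be done, "Since only one patient in the intervention group developed pressure ulcers". The control rate is "14.70% of the patients in the control group", which is five of 34.

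The Statistical Analysis section does not assign a test to this comparison. On the rank test it says: "Demographic quantitative data were compared between the groups by Mann Whitney U test". For the duration of ulcer development it names Kaplan-Meier, with no accompanying comparison test. For qualitative characteristics it allows Pearson chi-square or Fisher's exact test. The significance level is 0.05; sidedness is not stated.

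**The concern.** Time to pressure ulcer is the outcome in the trial's title, and 0.137 is the only p-value reported for it. The two figures compared, 16 days and 6.00 ± 2.0 days, are summaries of injured patients only, so the p-value appears to come from six people, one of whom makes up a whole arm.

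With 1 versus 5, a normal approximation to a rank statistic is unreliable, because the exact distribution has only six equally likely points. If 0.137 comes from that approximation, it lies below any value the exact test could produce. Readers would then not know that the comparison had no chance of reaching 0.05, and would take the non-significant result as information about the intervention.

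**Working it through.** **Inputs.** Arm sizes of 37 and 34 (table under Setting/Participants). Injury rates of 2.70% and 14.70%, intervention time of 16, control mean 6.00, SD 2.0, minimum 3, maximum 8, and p=0.137 (Results). Assumptions: times recorded in whole days, and a two-sided test.

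**Step 1: number injured.** 1/37 = 2.70% and 5/34 = 14.71%. The comparison is 1 versus 5.

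**Step 2: recover the control times.** Five whole-day values with mean 6.00 sum to 30. With minimum 3 and maximum 8, five sets are possible:

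| Set | Sample SD |
|---|---|
| 3, 3, 8, 8, 8 | 2.74 |
| 3, 4, 7, 8, 8 | 2.35 |
| 3, 5, 6, 8, 8 | 2.12 |
| 3, 5, 7, 7, 8 | 2.00 |
| 3, 6, 6, 7, 8 | 1.87 |

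Only 3, 5, 7, 7, 8 prints as 2.0. It has one tied pair.

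**Step 3: reproduce the printed figure.** Test 16 against these five values, with n1 = 1, n2 = 5 and N = 6.

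- U is at its extreme of 5. Its null mean is n1·n2/2 = 2.5, so the deviation is 2.5.
- Tie term: Σ(t³ − t) = 2³ − 2 = 6.
- Variance = (n1·n2/12) × [(N + 1) − Σ(t³ − t)/(N(N − 1))] = (5/12) × (7 − 6/30) = 2.833.
- z = 2.5/√2.833 = 1.485, two-sided p = 0.13749. This agrees with the printed 0.137.

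**Step 4: other tests of the same six values.**

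| Test | Two-sided p |
|---|---|
| Mann-Whitney, asymptotic, tie-corrected | 0.1375 |
| Mann-Whitney, asymptotic, no tie correction | 0.143 |
| Mann-Whitney, tie and continuity corrected | 0.235 |
| Log-rank | 0.126 |
| Breslow | 0.181 |
| Tarone-Ware | 0.148 |
| Permutation test on means | 0.167 |
| t-test | 0.010 |
| Exact rank test | 0.333 |

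Among these, only the first gives 0.137. A Kruskal-Wallis test is the same calculation with two groups and gives the same value.

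**Step 5: exact value.** Under the null hypothesis the single intervention patient is equally likely to hold any of six rank positions. Here that patient holds the highest. The one-sided p is 1/6 = 0.167. The two-sided p counts both ends: 2/6 = 0.333. No more extreme arrangement exists, so these are also the minima. Neither can equal 0.137.

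**Step 6: log-rank on all 71 patients.** This needs censoring times, which the document does not give. If nobody is censored before day 16, p = 0.066. Under simulated exponential censoring with means from 4 to 60 days, the median p ran from 0.045 to 0.070 and single draws from below 0.001 to 0.45. A value of 0.137 is possible but not typical.

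**The case against.** The strongest objection is that the test is inferred. The Results section names none, and the Statistical Analysis section points towards a time-to-event method for duration. A log-rank test on all 71 patients cannot be excluded. This stands. Agreement to the third decimal, together with a sentence that compares injured-patient summaries, makes Mann-Whitney likely but does not prove it.

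A reader might infer that 0.137 is a miscalculation. The documents do not support that: it is a correctly computed asymptotic p-value for the recovered data. The fault, if this test was used, is an unsuitable and unlabelled approximation.

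A reader might also infer that no analysis of these six values could reach significance. That is too broad. The floor of 0.333 and the zero power at 0.05 belong to the exact two-sided rank test. A permutation test on means gives 0.167, and a t-test gives 0.010, although a t-test is not defensible with a single patient in one arm.

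It is tempting to argue that the authors used exact tests for their other sparse comparisons, so that this figure breaks their own practice. The support is uneven. The 0.098 agrees with Fisher's exact test (0.0975; Pearson 0.069), and the 0.006 agrees with an exact test across weight groups (0.0065; Pearson 0.0072). The 0.003 agrees with an exact test in controls (0.0032) only if the three remaining injured control patients were obese. The sentence that prints 0.003 calls them overweight, and that allocation gives 0.120. The point here does not rely on this contrast.

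Finally, the result is non-significant at both 0.137 and 0.333, the document never calls 0.137 a trend, and its Conclusion does not cite the figure. All of that is true and limits the importance of the point. The ratio of the two p-values, about 2.4, should not be read as a measure of overstated evidence.

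**Conclusion.** The point holds in limited form. The only p-value for the title outcome has no stated test and agrees with a tie-corrected large-sample Mann-Whitney test of one versus five injured patients. If that is its source, the approximation is unsuitable: the exact two-sided value is 0.333 against the printed 0.137, and 0.333 is the lowest value that exact test can give. It could not have reached 0.05 whatever the data, so its non-significance says nothing about the intervention. The verdict at 0.05 does not change.

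This rests on whole-day times, a two-sided test, and the inference that Mann-Whitney was applied to injured patients only. The first two are reasonable readings; the third is likely but unconfirmed.

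**What to change.** State in the Statistical Analysis and Results sections which test gave p=0.137 and on which patients.

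- **If it was Mann-Whitney on the injured patients:** preferably delete the p-value and the statement of non-significance, and list the six injury days descriptively. Otherwise replace 0.137 with the exact two-sided 0.333 and add that this is the minimum attainable for an exact two-sided rank test of 1 versus 5.
- **If it was a log-rank test on all 71 patients:** say so.

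The cost is one number and one sentence. No new data are needed, and an exact p-value comes from the same test.

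### Higher injury risk in underweight patients is stated as a finding on 1 event in 2 patients; the BMI p-values fit only global tests, and two sentences disagree on which category holds three control events

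*Combined protocol and SAP*

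**What the plan says.** The BMI table in Setting/Participants lists 2 underweight patients (one per arm), 20 normal weight (8 intervention, 12 control), 31 overweight (17, 14) and 18 obese (11, 7), 71 in all.

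Statistical Analysis says: "The distribution of qualitative characteristics of the patients in the groups was analyzed using Pearson Chi-square test", with Fisher's exact test as the alternative, and judges results at the "95% confidence interval and $p<0.05$ significance level". It describes no comparison of one BMI category with another.

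Results first compares the arms on injury (p=0.098) and on time to injury (p=0.137). It then reports one underweight and one normal-weight injury in controls, together with "three obese patient in the control group and one obese patient in the intervention group, the difference between them was statistically significant" (p=0.006). The next sentence covers the control group alone and again counts one underweight and one normal-weight patient, but now "three patients with overweight developed pressure injuries and the difference between them was statistically significant" (p=0.003). Results adds that injury by BMI could not be assessed in the intervention arm.

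Two general risk statements follow. Results says "The risk of pressure injury development is higher in underweight and obese patients, and less in overweight patients", and Conclusion says "risk of pressure injury development is higher in low-weight and obese patients, while it is less in overweight patients". No rate, interval or contrast is given for any BMI category.

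**The concern.** A directional claim about each of three BMI categories needs a result for each of them. The document prints two p-values on BMI, and both look like global tests. A global test can be significant because of one pair of categories and say nothing about a third. The underweight category has two patients in the whole trial, yet its higher risk is a headline conclusion.

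Two further features make the result hard to use. The p=0.006 sentence comes straight after two arm comparisons, names both arms and refers to a difference between them, so it reads like an effect of the intervention. And the three control events behind the obese and overweight statements are assigned to different categories in consecutive sentences. If the second sentence is the correct one, those statements lose their support.

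**Working it through.** **Inputs.** Category sizes come from the table in Setting/Participants and events from Results. Tests are taken as two-sided, which the document does not state.

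| Category | Control | Intervention | Pooled, three events in obese | Pooled, three events in overweight |
|---|---|---|---|---|
| Underweight | 1/1 | 0/1 | 1/2 | 1/2 |
| Normal weight | 1/12 | 0/8 | 1/20 | 1/20 |
| Overweight | 0/14 or 3/14 | 0/17 | 0/31 | 3/31 |
| Obese | 3/7 or 0/7 | 1/11 | 4/18 | 1/18 |

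**1. Reproduce the printed p-values.** For the Fisher-Freeman-Halton test, a table with events e_i in n_i patients has probability ∏C(n_i, e_i) / C(N, E). The p-value sums this over all tables no more probable than the one observed.

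- Pooled, events in obese: observed weight C(2,1)·C(20,1)·C(31,0)·C(18,4) = 2·20·1·3060 = 122,400. Tables with weight no larger sum to 924,969. With C(71,6) = 143,218,999, p = 924,969/143,218,999 = 0.0065 (printed 0.006).
- Controls, events in obese: observed weight 1·12·1·35 = 420. Tables with weight no larger sum to 896. With C(34,5) = 278,256, p = 896/278,256 = 0.0032 (printed 0.003).
- Pearson tests on the same tables give 0.0072 and 0.0046, a poorer match.
- Events in overweight: exact p = 0.272 pooled and 0.120 in controls (Pearson 0.170 and 0.048). None of these matches a printed value.

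**2. Is p=0.006 an arm comparison?** Injury by arm, 1/37 against 5/34, gives Fisher p=0.0975, the printed 0.098. Comparing the BMI mix of the six injured patients between arms gives p=1.0. Neither is 0.006.

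**3. Underweight, 1 of 2.**

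- Clopper-Pearson 95% CI: lower limit 1 − √0.975 = 0.013, upper limit √0.975 = 0.987.
- Fisher against the rest (5/69): with 6 events in 71 patients, P(both underweight injured) = C(6,2)/C(71,2) = 15/2485 = 0.006 and P(one injured) = 6·65/2485 = 0.157. The sum is p=0.163. It is the same under either placement of the three events.
- With the events in obese patients, the pairwise p-values are 0.061 against overweight, 0.177 against normal weight and 0.447 against obese. The first is 2/33, the smallest p-value possible with one event in 33 patients, so it does not show that there is no difference.
- With the underweight row removed, the global exact test is still 0.0076 pooled and 0.011 in controls. The significance does not depend on these two patients.

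**4. The other two statements, with events in obese (pooled, Fisher, unadjusted).** Obese against the rest, 4/18 v 2/53: p=0.033. Overweight against the rest, 0/31 v 6/40: p=0.032. Obese against overweight, 4/18 v 0/31: p=0.014. With the events in overweight patients, each of these three gives p=1.0.

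**The case against.** The strongest defence is that the authors may have used a category-level step that they did not report. In the pooled table the adjusted residuals are +2.14 underweight, −0.65 normal weight, −2.25 overweight and +2.43 obese. The sentence in Results names exactly the three categories beyond ±1.96. That would explain the claim, but it does not rescue the underweight part. The expected count there is 2·6/71 = 0.17, far too small for a normal approximation, and the exact test of the same contrast gives 0.163.

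Some of the defence stands. The Statistical Analysis wording on Pearson or Fisher tests could be read as covering injury by BMI group. The p=0.003 sentence already says that it concerns the control group, so only p=0.006 is ambiguous in scope. Event counts and denominators are both printed, so a reader can rebuild the rates. The remarks might also be meant as description, although they are worded as general risk statements, follow results called significant, and close the report.

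A reader might go further and infer that two patients could never show a higher risk. That is not so: 2 of 2, with the other five events unchanged, would give C(7,2)/C(71,2) = 21/2485 = 0.008 against the rest. The weakness is the observed 1 of 2. Nor do the documents support the inference that the whole BMI statement is empty, because the obese and overweight parts have post hoc support if the first event sentence is right.

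**Conclusion.** The point holds. The claim of higher risk in underweight patients is not established: 1 of 2, interval 1.3% to 98.7%, and no exact underweight contrast below 0.05. It would be equally wrong to conclude that underweight patients have no higher risk.

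The obese and overweight statements have unadjusted, post hoc support (p=0.033 and 0.032 against the rest), but only if the three control events were in obese patients. The reproduction of both printed p-values points that way, but it cannot replace the patient records.

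The p=0.006 result should not be taken as evidence for the intervention; the arm comparison is the printed 0.098, which this point leaves unchanged.

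These conclusions assume two-sided tests, the printed category sizes as denominators, and that 0.006 and 0.003 come from global exact tests. The last is inferred from the match.

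**What to change.** 1. Check the records of the three control patients and reconcile the two sentences. If the events were in overweight patients, recompute both p-values and remove the obese and overweight statements.
2. Name the test and table behind p=0.006 and p=0.003, and any category-level method used. Label p=0.006 as injury by BMI category, both arms pooled, exploratory.
3. Remove the underweight risk claim from Results and Conclusion. Report 1 of 2 (exact 95% CI 1.3% to 98.7%) as description only.
4. If obese is confirmed, keep the obese-higher and overweight-lower statements only as post hoc and exploratory, with the unadjusted p-values from step 4 of the check. Add counts and exact 95% CIs: underweight 1/2 (1.3% to 98.7%), normal weight 1/20 (0.1% to 24.9%), overweight 0/31 (0% to 11.2%), obese 4/18 (6.4% to 47.6%). No particular multiplicity method is required, provided the results are labelled in this way.

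The cost is a check of three records, rewording in two sections and one small table. The drawback for the authors is a weaker BMI message.

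### The Conclusion recommends personalised over two-hourly repositioning without saying that the arm comparison (1/37 vs 5/34, p=0.098) missed the 0.05 level and rests on six injured patients

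*Combined protocol and SAP*

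**What the plan says.** The Statistical Analysis section sets the criterion: "The results were evaluated at 95% confidence interval and $p<0.05$ significance level".

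The Results section then reports, for the two arms:

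- Incidence: "Pressure injuries developed in 2.70% of the patients in the intervention group and 14.70% of the patients in the control group". The verdict on that comparison is "the difference between them wasn't statistically significant ($p=0.098".
- Time to injury, the outcome named in the title: day 16 for the one injured intervention patient against a mean of 6.00 days (SD 2.0) in the control arm. The verdict is "the difference between them was not statistically significant ($p=0.137".
- Injuries by BMI group, with p=0.006: "one underweight, one normal weight, and three obese patient in the control group and one obese patient in the intervention group". The next paragraph gives p=0.003 within the control arm, but there it is "three patients with overweight developed pressure injuries", so the document is inconsistent about which BMI group those three patients belong to.

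The Conclusion says that "the frequency of position changes should be done with a personalized program for each patient, not at routine two-hour intervals". The same sentence adds that risk is higher in low-weight and obese patients and lower in overweight patients. It gives no p-value, event count, interval or limitation.

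**The concern.** A statement of what care should be replaces one schedule with another, so it needs a comparison of the schedules to support it. The only incidence comparison of the arms fails the criterion that the document set for itself, and it rests on six patients. The document claims neither non-inferiority nor equivalence, so the sentence cannot be read as saying that the personalised schedule was shown to be no worse and may be preferred on other grounds.

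The Conclusion is the part most likely to be lifted into a summary or into ward practice. A reader who stops there would believe that the trial had shown two-hourly turning to be the wrong policy for intensive and palliative care patients. The data are compatible with a large benefit and also with a small excess of injuries.

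**Working it through.** **Inputs.** Arm sizes are 37 and 34 (BMI table under Setting/Participants). The Results percentages give 0.0270 × 37 = 1.0 and 0.1470 × 34 = 5.0. The counts are therefore 1/37 and 5/34, six injured patients in all.

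**The document's own p-value.** Given six injured patients among 71, the number in the intervention arm is hypergeometric: P(k) = C(37,k) × C(34,6−k) / C(71,6). This gives P(0)=0.0094, P(1)=0.0719 and P(6)=0.0162; every other outcome is more probable than the observed k=1. Two-sided Fisher p = 0.0094 + 0.0719 + 0.0162 = 0.0975, which rounds to the stated 0.098. The stated effect size also reproduces: Pearson chi-square is 3.300, and phi = √(3.300/71) = 0.216.

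**Other tests of the same table.** Pearson without correction gives p=0.069 and with Yates correction p=0.165; one-sided Fisher gives 0.081. None is below 0.05.

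**Size and precision.**

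- Risk difference: 1/37 − 5/34 = 0.0270 − 0.1471 = −0.120.
- Wilson 95% limits: 0.0048 to 0.1382 (intervention) and 0.0645 to 0.3013 (control).
- Newcombe lower limit: −0.120 − √[(0.0270−0.0048)² + (0.3013−0.1471)²] = −0.276.
- Newcombe upper limit: −0.120 + √[(0.1382−0.0270)² + (0.1471−0.0645)²] = +0.018.
- Odds ratio: (1×29)/(36×5) = 0.16, exact 95% interval 0.003 to 1.59.

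**Fragility.** One more control injury (1/37 vs 6/34) gives Fisher p=0.049; one fewer (1/37 vs 4/34) gives p=0.187.

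**Stratifying by the four BMI groups.** The exact conditional two-sided test of arm within BMI group gives p=0.068 if the three disputed control patients were obese and p=0.099 if they were overweight.

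**Time to injury.** If times are whole days, the only five control values with minimum 3, maximum 8, mean 6.00 and SD 2.0 are 3, 5, 7, 7 and 8. Against day 16, the uncorrected asymptotic Mann-Whitney test gives p=0.1375, which agrees with 0.137. If that is the test used, it compares one injured patient with five and ignores everyone who was not injured. The smallest exact two-sided p that such a comparison can give is 2/6 = 0.333, so it could not have supported either schedule.

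**The two significant p-values.** Exact tests of BMI category by injury give:

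| Reading of the three control patients | Both arms pooled | Control arm only |
|---|---|---|
| Obese | 0.0065 | 0.0032 |
| Overweight | 0.27 | 0.12 |

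The obese reading matches the stated 0.006 and 0.003. These tests compare BMI groups. On that reading, the arm comparison among obese patients is 1/11 vs 3/7, Fisher p=0.245. BMI group by arm among the six injured patients gives p=1.0. Neither reproduces 0.006.

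**The case against.** The strongest reply is that nothing is hidden. Results gives both non-significant p-values, calls the effect low to medium, and stands just above the Conclusion in a very short document; the Statistical Analysis section says that "only one patient in the intervention group developed pressure ulcers". This stands as far as it goes: it is a fault of interpretation in one sentence, and no test or reported figure is wrong because of it. It does not correct a Conclusion that omits the result.

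A second reply is that the authors may have reasoned from BMI, not from the arms: risk differs by BMI group, so turning should be individualised. The second half of the Conclusion sentence fits that reading. But unequal risk between BMI groups does not show that a BMI-based schedule lowers it, and the sentence rejects the two-hour interval outright.

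Third, the stratified result depends on the test. On the obese reading, the uncorrected Mantel-Haenszel test gives p=0.038 and the one-sided exact test 0.047, against 0.102 with continuity correction. On the overweight reading the three are 0.070, 0.080 and 0.165. An uncorrected asymptotic test is unreliable with six events, and a one-sided test is not the usual reading of the stated level. The statement that stratifying changes nothing therefore applies to the two-sided exact test.

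Fourth, the Mann-Whitney origin of p=0.137 is inferred. The document names Kaplan-Meier for development time, and a log-rank result cannot be checked without follow-up times. This is fair; the main point does not need it.

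**Conclusion.** The concern holds. The Conclusion makes an unqualified recommendation that the arm comparison does not support at the document's own 0.05 level: 1/37 vs 5/34, p=0.098, risk difference −12.0 points (95% interval −27.6 to +1.8), six injured patients. The point estimate favours the intervention, and nothing here shows that it fails; the trial is inconclusive on incidence.

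The main result needs only the reported counts and a two-sided reading of the 0.05 level, which the document does not spell out. Two further points are assumptions. That the control arm was turned every two hours is inferred from the Conclusion, since neither arm's schedule is described. The account of the 0.006 and 0.003 values assumes that the three disputed control patients were obese.

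**What to change.** Replace the recommendation with a statement of what was found, for example:

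> Fewer patients in the intervention arm developed a pressure injury (1/37 vs 5/34; risk difference −12.0 percentage points, 95% CI −27.6 to +1.8), but the difference did not reach the stated 0.05 level (p=0.098). With six injured patients, the trial is inconclusive on which schedule is better for incidence or for time to injury.

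This takes no position on which schedule is right. The cost is one reworded sentence and one confidence interval computed from counts already reported. No new data or analysis is needed, but the message becomes less favourable to the intervention.

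### The Conclusion replaces two-hour turning with personalised programs, but no arm difference is shown and the significant p-values test BMI, not the schedule

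*Combined protocol and SAP*

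**What the plan says.** The Conclusion states that "the frequency of position changes should be done with a personalized program for each patient, not at routine two-hour intervals", and adds that risk is higher in low-weight and obese patients and lower in overweight patients. The title, which opens "THE EFFECT OF REPOSITIONING FREQUENCY DETERMINED ACCORDING" and goes on to name body mass index, gives the only individualising factor the document describes. Two-hour turning is named only in the Conclusion.

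Results gives three arm comparisons, all non-significant: incidence 2.70% against 14.70% (p=0.098), time to injury (p=0.137) and injury site (p=0.143). On time, it says "Injury development time was 16 days in the intervention group" and gives 6.00 ± 2.0 days for control, range 3 to 8.

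Two results are reported as significant. The first lists control injuries as one underweight, one normal weight and three obese, then ends "one obese patient in the intervention group, the difference between them was statistically significant ($p=0.006". The second covers the control arm alone, p=0.003. For the intervention arm, Results says that "the development of pressure injuries according to body mass index could not be evaluated". Statistical Analysis sets the threshold at p<0.05.

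**The concern.** A directive to abandon routine two-hour turning needs evidence that the alternative schedule does better. None of the reported arm comparisons provides it, and a program for each patient is wider than four BMI categories.

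The sentence carrying p=0.006 lists injuries by arm as well as by BMI, so it can be read as a significant arm effect and taken as support for the Conclusion. If it is really a test of BMI, it says who is at risk and nothing about which schedule is better.

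The control-arm sentence adds a contradiction. It refers to "three patients with overweight developed pressure injuries and the difference between them was statistically significant ($p=0.003", whereas the paragraph before it places those three injuries in obese patients. The two paragraphs disagree on who was injured.

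**Working it through.** **Inputs.** Denominators (intervention/control) from the table in Setting/Participants: underweight 1/1, normal weight 8/12, overweight 17/14, obese 11/7; total 37/34. Injuries from Results: intervention one obese; control one underweight, one normal weight, three obese (or three overweight, as the later paragraph says).

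**1. The reported arm comparison.** 1/37 = 2.70% and 5/34 = 14.7%. Two-sided Fisher exact: 13,965,160 / 143,218,999 = 0.0975, matching 0.098. Uncorrected Pearson chi-square is 3.300 (p=0.069), and √(3.300/71) = 0.216, matching the stated effect size. Wilson limits are 0.5% to 13.8% and 6.4% to 30.1%. Newcombe's method then gives a difference of -12.0 points, 95% interval -27.6 to +1.8.

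**2. What p=0.006 and p=0.003 test.** Fisher-Freeman-Halton exact test of BMI category against injury:

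| Table | Injuries/n (under, normal, over, obese) | Exact p | Pearson p |
|---|---|---|---|
| Arms pooled, obese reading | 1/2, 1/20, 0/31, 4/18 | **0.0065** | 0.0072 |
| Control only, obese reading | 1/1, 1/12, 0/14, 3/7 | **0.0032** | 0.0046 |
| Arms pooled, overweight reading | 1/2, 1/20, 3/31, 1/18 | 0.272 | 0.170 |
| Control only, overweight reading | 1/1, 1/12, 3/14, 0/7 | 0.120 | 0.048 |

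The exact tests on the obese reading give 0.006 and 0.003; the overweight reading gives neither. The arm readings tried do not give 0.006: arm by BMI among the injured, Pearson 0.74; arm within each BMI category, Fisher 1.0, 1.0, 1.0 and 0.245.

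**3. What p=0.137 tests.** Assume whole days. Five control times with minimum 3, maximum 8, mean 6.00 and SD 2.0 can only be 3, 5, 7, 7, 8. Mann-Whitney of 16 against these, with normal approximation, tie correction and no continuity correction: U = 5, expected 2.5, variance (5/12)(7 − 6/30) = 2.833, z = 2.5/1.683 = 1.485, p = 0.1375. This matches 0.137. With one patient against five, the smallest exact two-sided p is 2/6 = 0.333, so such a test says little about the arms.

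**4. Arms within BMI categories (this review's own tests; the document reports none).** Obese reading:

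| Category | Intervention | Control | Fisher p | Smallest attainable |
|---|---|---|---|---|
| Underweight | 0/1 | 1/1 | 1.0 | 1.0 |
| Normal weight | 0/8 | 1/12 | 1.0 | 0.40 |
| Overweight | 0/17 | 0/14 | no events | none |
| Obese | 1/11 | 3/7 | 0.245 (Pearson 0.093) | 35/3060 = 0.011 |

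Only the obese category could have reached 0.05.

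Stratified by BMI, expected intervention injuries are 1(1/2) + 8(1/20) + 11(4/18) = 0.50 + 0.40 + 2.44 = 3.34, against 1 observed. The variance is 0.25 + 0.24 + 0.783 = 1.273. Cochran-Mantel-Haenszel (CMH): (1 − 3.34)²/1.273 = 4.32, p=0.038 uncorrected, 0.102 corrected; exact 0.068.

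On the overweight reading, 0/17 against 3/14 gives Fisher 0.081 and Pearson 0.045. The stratified tests give exact 0.099 and CMH 0.070 uncorrected, 0.165 corrected. No exact test reaches 0.05 on either reading, although some uncorrected large-sample tests do.

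**The case against.** The strongest objection concerns p=0.137. Statistical Analysis says Kaplan-Meier analyses were performed for injury time and assigns Mann-Whitney only to demographic data. A log-rank test on all 71 patients depends on censoring times that are not reported. With the reconstructed event times and one assumed censoring day per arm (4 to 30), it can give anything from below 0.01 to 0.82, including 0.136 (intervention censored at day 6, control at day 8 to 14). So the p-value alone cannot identify the test. This stands as a reason to check the output before labelling. It does not help the Conclusion, because p=0.137 is non-significant whichever test produced it.

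Second, the document never calls p=0.006 an arm effect, and it goes on to interpret the BMI results as BMI risk, in Results and in the Conclusion's second clause. That is fair. The concern is an ambiguous sentence, and stating what was tested removes the ambiguity.

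Third, BMI-set turning is a form of personalisation, and this short document describes neither arm's schedule. That softens the point about breadth but leaves the missing arm difference untouched.

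Fourth, the overweight label is probably a slip that the surrounding text corrects. It is, and it needs only an erratum.

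Finally, the estimate favours the intervention and Results openly reports non-significance. Both are true; the fault lies in the recommendation drawn.

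**Conclusion.** The concern holds. The recommendation to replace two-hour turning is not established: the arm comparison rests on six injuries, and its interval runs from a 27.6-point reduction to a 1.8-point increase. The finding is inconclusive, not negative. The BMI-stratified results (0.038 to 0.102, depending on method) are post hoc and too method-dependent to change this.

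The reading of p=0.006 and p=0.003 as tests of BMI against injury is strong, because both match to the stated precision on one consistent set of counts. The reading of p=0.137 as a comparison of injured patients only is likely but less certain, since it assumes whole days and a test not named for that outcome. The obese label is favoured by both p-values and by the document's own statement that risk is lower in overweight patients; source data should settle it.

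**What to change.** - **Conclusion.** Say that a repositioning frequency determined by BMI was not shown to differ from control (1/37 against 5/34, difference -12.0 points, 95% interval -27.6 to +1.8, p=0.098). Add that with six injuries the result is inconclusive and does not establish replacing two-hour turning.
- **P-values.** After checking the output, name the test and the patients beside each: p=0.006, BMI category against injury, arms pooled; p=0.003, the same within control; p=0.137, injured patients only, if the output confirms it.
- **Label.** After a source-data check, change the three overweight control injuries to obese.
- **Table.** Show injuries/n by arm and BMI category.

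The cost is rewording, three labels, one source-data check and one small table. No new data are needed. The price is a narrower claim.
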